**Table 4-8 AE imputation example scenarios**

Partial AE start date	Treatment start date	Relationship	Imputation Calculation	Imputed Date
12mmyyyy	20OCT2001	Uncertain	NC	<blank>
ddmmm2000	20OCT2001	Before	( D )	01JUL2000
ddmmm2002	20OCT2001	After	( E )	01JAN2002
ddmmm2001	20OCT2001	Uncertain	( B )	21OCT2001
ddSEP2001	20OCT2001	Before	( C )	15SEP2001
ddOCT2001	20OCT2001	Uncertain	( B )	21OCT2001
ddNOV2001	20OCT2001	After	( A )	01NOV2001

#### 4.8.2 Concomitant medication date imputation

The imputation of the start date of concomitant medication will follow the same conventions as for AE date. Partial concomitant medication end dates will not be imputed.

#### 4.8.3 Incomplete date of initial diagnosis of cancer, date of first recurrence/progression and date of most recent recurrence

Missing day is defaulted to the 15th of the month and missing month and day is defaulted to 01-Jan.

#### 4.8.4 Incomplete date for anti-neoplastic therapies

##### Prior therapies

###### Start date:

The same rule which is applied to the imputation of AE/concomitant medication start date will be used with the exception that for scenario (B) will be replaced to be 'start date of study drug -1'.

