- Patients who have been treated with chemotherapy, with biological therapy or other investigational agent must have discontinued the treatment at least 2 weeks (14 days) prior to starting study drug. In case last chemotherapy contains nitrosourea or mitomycin C, the treatment must be discontinued at least 6 weeks prior to the first dose of study drug.
 - Patients, if previously treated with crizotinib must discontinue treatment at least 1 week (7 days) prior to the first dose of study drug.
- 7a. Patient must meet the following laboratory values at the screening visit:
- Absolute Neutrophil Count $\geq 1.5 \times 10^9/L$
 - Platelets $\geq 75 \times 10^9/L$
 - Hemoglobin (Hgb) ≥ 8 g/dL
 - Serum creatinine < 1.5 mg/dL and /or calculated creatinine clearance (using Cockcroft-Gault formula) ≥ 30 mL/min
 - Total bilirubin $\leq 1.5 \times$ ULN except for patients with Gilbert's syndrome who may only be included if total bilirubin $\leq 3.0 \times$ ULN or direct bilirubin $\leq 1.5 \times$ ULN
 - Aspartate transaminase (AST) $\leq 3 \times$ ULN, except for patients with liver metastasis, who are only included if AST $\leq 5 \times$ ULN
 - Alanine transaminase (ALT) $\leq 3 \times$ ULN, except for patients with liver metastasis, who are only included if ALT $\leq 5 \times$ ULN
 - Alkaline phosphatase (ALP) $\leq 5.0 \times$ ULN
 - Serum amylase $\leq 2 \times$ ULN
 - Serum lipase \leq ULN
 - Fasting plasma glucose ≤ 200 mg/dL (≤ 11.1 mmol/L)
8. Patient must have the following laboratory values within normal limits or corrected to within normal limits with supplements during screening:
- Potassium
 - Magnesium
 - Phosphorus
 - Total calcium (corrected for serum albumin)
9. Patient has life expectancy ≥ 6 weeks.
10. Patient has a WHO performance status 0-2.
11. Patient has the ability to understand and provide signed informed consent.
12. Willingness and ability to comply with scheduled visits, treatment plans, laboratory tests and other study procedures.

Patients in Arm 1 to 4 must also meet the following inclusion criteria:

13. Patients must have active brain metastases from NSCLC, confirmed by Gadolinium-enhanced MRI without concomitant leptomeningeal carcinomatosis. Dose of steroids must be stable for 5 days before the baseline brain MRI.

Note: An active brain lesion is a lesion free of any local treatment (like stereotactic radiosurgery or whole brain radiation). The following lesions are considered active:

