5.3 Exclusion criteria

Patients eligible for this study must not meet **any** of the following criteria:

1. Patient with a history of treatment with ceritinib. Patient with known hypersensitivity to any of the excipients of ceritinib (microcrystalline cellulose, mannitol, crospovidone, colloidal silicon dioxide and magnesium stearate).
2. Patients who need whole brain radiation to control the brain metastases. Patients will not be eligible unless treated brain lesions are progressive or new brain lesions are observed since the post whole brain radiation therapy MRI.
3. In case active brain lesions (single or not) require local treatment but other active brain lesions do not and are not treated, patients will be excluded only if the local treatment (neurosurgical treatment or Stereotactic Radiosurgery) for the brain metastases is conducted within 2 weeks prior to starting study drug. Patients must have recovered from relevant toxicities related to these procedures to grade ≤ 1 (CTCAE v 4.03) prior to receiving the first dose of study drug.
4. Planning of any brain local treatment (including but not limited to surgery, stereotactic radiosurgery, whole brain radiation, intrathecal chemotherapy) following the administration of the first dose of study drug.
5. Patient who has received thoracic radiotherapy to lung fields ≤ 4 weeks prior to starting the study treatment or patients who have not recovered from radiotherapy-related toxicities. For all other anatomic sites (including radiotherapy to thoracic vertebrae and

- ribs) radiotherapy ≤ 2 weeks prior to starting the study treatment or has not recovered from radiotherapy-related toxicities. Palliative radiotherapy for bone lesions ≤ 2 weeks prior to the first dose of study drug is allowed.
6. Patient has had major surgery (e.g., intra-thoracic, intra-abdominal or intra-pelvic) within 4 weeks prior to the first dose of study drug or has not recovered from side effects of such procedure. Video-assisted thoracic surgery (VATS) and mediastinoscopy will not be counted as major surgery and patients can receive study treatment ≥ 1 week after the procedure.
 7. Patient with a concurrent malignancy or history of a malignant disease other than NSCLC that has been diagnosed and/or required therapy within the past 3 years. Exceptions to this exclusion include the following: completely resected basal cell and squamous cell skin cancers, and completely resected carcinoma *in situ* of any type.

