## Prior anti-cancer therapy

Prior anti-neoplastic (anti-cancer) therapy will be listed in three separate categories: 1. medications, 2. radiotherapy, and 3. surgery.

The number and percentage of patients who received any prior anti-neoplastic medications, prior antineoplastic therapy Crizotinib, prior anti-neoplastic radiotherapy, prior anti-neoplastic radiotherapy to the brain, or prior anti-neoplastic surgery will be summarized by study arm and for all patients.

Prior anti-neoplastic medications will be summarized by study arm. Summaries will include chemotherapy (medication) setting, other therapy (medication) setting, number of prior regimens (crizotinib and other), therapy type, setting, best response at last treatment, time from last treatment start to progression and duration of last treatment best response. Prior antineoplastic medications will also be summarized by ATC class, preferred term and study arm. Prior antineoplastic therapy crizotinib will be summarized by study arm and includes setting, best response at last crizotinib treatment, time from last crizotinib treatment start to progression, duration of last crizotinib treatment best response and reason for discontinuation of last crizotinib treatment.

For radiotherapy and radiotherapy to the brain, time since last radiotherapy end to treatment start, locations, setting and method of last therapy will be summarized. For prior surgery, time since last surgery, procedure and residual disease at last surgery will be summarized. ATC class and preferred term will also summarize steroid use at the start of study drug.

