###### End date:

Imputed date = min (start date of study drug, last day of the month), if day is missing;

Imputed date = min (start date of study drug, 31DEC), if month and day are missing.

If the end date is not missing and the imputed start date is after the end date, use the end date as the imputed start date.

If both the start date and the end date are imputed and if the imputed start date is after the imputed end date, use the imputed end date as the imputation for the start date.

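### Two prior-therapy date rules in SAP 4.8.4 can give a negative time from crizotinib start to progression and 0 days since brain radiotherapy

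*SAP*

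**What the plan says.** SAP 4.8.4 handles incomplete dates of prior anti-neoplastic therapy.

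- **Start date.** The rule for "AE/concomitant medication start date will be used with the exception that for scenario (B) will be replaced to be" the start of study drug minus 1 day. Tables 4-6 and 4-7 define the scenarios. (B) applies when the start year is the treatment year and the month is either missing or the treatment month. (C), a known earlier month, goes to the 15th. (D), an earlier year without month, goes to 1 July.
- **End date.** For a partial date that lacks only the day, the SAP writes "Imputed date = min (start date of study drug, last day of the month), if day is missing". A year-only end is treated in the same way, with the end of the year in place of the end of the month: "Imputed date = min (start date of study drug, 31DEC), if month and day are missing".
- **Order check.** With a known end date, if "the imputed start date is after the end date, use the end date as the imputed start date". If both dates are imputed and out of order, "use the imputed end date as the imputation for the start date".

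SAP 2.3 (Prior anti-cancer therapy) tabulates "time from last crizotinib treatment start to progression, duration of last crizotinib treatment best response", among other crizotinib items. For radiotherapy, and for brain radiotherapy separately, it tabulates the time from the end of the last course to the start of treatment.

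In the protocol, inclusion criterion 6a says that patients "if previously treated with crizotinib must discontinue treatment at least 1 week (7 days) prior to the first dose of study drug". Exclusion criterion 5 rules out, for sites other than the lung fields, "radiotherapy ≤ 2 weeks prior to starting the study treatment", with an exception for palliative bone radiotherapy. Exclusion criterion 3 sets a 2-week limit for surgery or radiosurgery to brain lesions.

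**The concern.** The (B) start and the end-date cap both refer to the first dose of ceritinib and take no account of the protocol's washout windows. An eligible patient cannot have started crizotinib the day before first dose, nor finished brain radiotherapy on the day of first dose.

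The order check in 4.8.4 compares start with end only. Neither 4.8.4 nor 4.8.8 compares the start with the date of progression on that therapy. Yet 4.8.8 has branches for a prior therapy that ended in a month or year after the progression, so the SAP itself expects progression before the end of the course. In that situation a start that has been moved to the end date falls after the progression.

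Time from crizotinib start to progression tells a reader how refractory the pretreated patients were. Time since brain radiotherapy helps a reader judge whether an intracranial response could be a late radiation effect. Both are descriptive, but a printed negative time, or a 0-day gap that contradicts eligibility, would mislead or raise queries.

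**Working it through.** **Reproducing the plan's own examples.** Tables 4-6 and 4-7, coded as a date rule, return all seven rows of SAP Table 4-8. For instance, a year-only 2001 start with treatment start 20 Oct 2001 gives 21 Oct 2001 under (B). With the prior-therapy exception the same case gives 19 Oct 2001.

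**Start dates.** Assume first dose on 20 Oct 2016 and progression on crizotinib on 10 Sep 2016. Time to progression is the plain difference, progression minus start.

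| Recorded start | Recorded end | Imputed start | End used | Time to progression |
|---|---|---|---|---|
| 2016 only (B) | 30 Sep 2016 | 19 Oct, moved to 30 Sep | 30 Sep 2016 | -20 days |
| 2016 only (B) | 2016 only | 19 Oct 2016 | 20 Oct 2016 | -39 days |
| Mar 2016 (C) | 30 Sep 2016 | 15 Mar 2016 | 30 Sep 2016 | +179 days |
| 2015 only (D) | 30 Sep 2016 | 1 Jul 2015 | 30 Sep 2016 | +437 days |

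In the first row the true value could be anything from 0 days to 253 days (1 Jan to 10 Sep). Adding 1 day, as for the efficacy durations, would give -19 and -38, still negative. (C) and (D) use mid-period dates and are not placed next to first dose. The check against progression is absent for them too, however. A (D) start with an end before 1 July of that year is also moved to the end date, so a progression before that end would give a negative value. The bound proposed below covers this narrow case.

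**End dates.** Gap = first dose minus imputed end, computed for each of the 366 possible first-dose days in 2016.

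- End in the first-dose month, or year-only in the first-dose year: the cap applies, and the gap is 0 days for every first-dose date.
- Day missing in the preceding month: the end is that month's last day, so the gap equals the day of the month of first dose, 1 to 31. It is 14 days or less for 12 × 14 = 168 of 366 dates (45.9%), and under 7 days for 12 × 6 = 72 of 366 (19.7%).
- Day missing two months back: the gap is 30 to 62 days, never inside a 7- or 14-day window.
- Year-only in the previous year: the gap is 14 days or less for 14 of 366 dates (3.8%).

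For comparison, a patient with first dose on 20 Oct 2016 and brain radiotherapy recorded as ended in 2016, if eligible, has a true gap between 15 days (5 Oct) and 293 days (1 Jan). The rule prints 0.

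**Number of patients.** The share of partial dates is not given. Amendment 6 gives 42 + 40 = 82 patients in Arms 1 and 2, and 42 + 12 = 54 in Arms 1 and 3. If 1% to 5% had a partial date of the relevant kind (an assumption), that is 0.8 to 4.1 and 0.5 to 2.7 patients. These counts cover any partial date. Only some of those dates would fall in the cells above.

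**The case against.** The case for leaving the rule alone is fair in several respects. A negative time needs several things together: crizotinib started in the same calendar year as ceritinib, the start month missing (a start in the ceritinib month is hardly plausible with a 7-day washout), and progression before the substituted start. SAP 4.8.1 says that partial adverse-event dates should be sent back to the investigator, and protocol 9.4 provides for queries on missing values, so few should remain. A median is unlikely to move, though a minimum could. A radiotherapy end placed too late makes the gap look shorter, which makes a reader more cautious about the drug effect. Eligibility also requires irradiated lesions to have grown before they count as active. Palliative bone radiotherapy close to first dose is allowed, so a short gap is not always a contradiction.

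All of this stands, and it limits the importance of the point. It does not make the stated rules correct: in the cells shown they give impossible or ineligible values, and nothing in 4.8.4 catches them.

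A reader might also infer that 4.8.4 puts every missing date at the latest day inside the washout, or that the history tables will show one-day courses. The documents do not support either. Among starts only (B) is placed next to first dose, and ends two or more months back stay clear of the 7- and 14-day windows. SAP 2.3 names no course duration for the crizotinib or radiotherapy tables, so a collapsed course would be seen only in listings.

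**Conclusion.** The point holds in a narrow form. A (B) start can give a negative time from last crizotinib start to progression. A partial radiotherapy end in the first-dose month, or year-only in the first-dose year, always gives 0 days. That lies inside the 2-week exclusion for brain radiotherapy, and a missing day in the preceding month can fall inside it as well.

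The illustrations rest on assumed dates, and the 45.9% on first doses spread evenly over the days of 2016. The number of affected patients cannot be known from the documents and is probably small.

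It would be wrong to infer that the efficacy results are at risk. Arm allocation uses prior therapy as yes or no, and ORR, DCR, PFS and OS do not use these dates. The consequence is confined to descriptive baseline tables and listings. This is a low-priority correction, worth making because it is cheap.

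**What to change.** In SAP 4.8.4:

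1. **Starts.** An imputed start may not be later than the earliest known progression, response or end date of that regimen. For scenario (B), use the midpoint between the earliest day the partial date allows (or the end of the previous regimen, if later) and the earliest of those known dates. In the first example this is the midpoint of 1 Jan and 10 Sep 2016, which is 6 May 2016, and the time to progression becomes +127 days.
2. **Ends.** Impute to the midpoint of the days that fit the partial date, are not before a known start of that course, and lie outside the protocol's own window for that therapy. The windows are 7 days for crizotinib; 14 days for chemotherapy, biologic or investigational agents; 6 weeks for nitrosourea or mitomycin C; 4 weeks for lung-field radiotherapy; and 2 weeks for other radiotherapy or local brain treatment. Palliative bone radiotherapy has no such cap. In the radiotherapy example (known start absent) the days are 1 Jan to 5 Oct 2016, the midpoint is 19 May, and the gap is (15 + 293) / 2 = 154 days.
3. **Exceptions.** The analysis set includes every dosed patient, so the cap must not hide a deviation. If no admissible day exists, or a deviation is recorded, do not apply the cap, and flag the record as a possible deviation.
4. **Listings.** Flag every imputed prior-therapy date.

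The cost is SAP wording, one derivation macro and a rerun of the affected baseline tables and listings. No new data are needed.

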###### End date:

Imputed date = min (start date of study drug, last day of the month), if day is missing;

Imputed date = min (start date of study drug, 31DEC), if month and day are missing.

If the end date is not missing and the imputed start date is after the end date, use the end date as the imputed start date.

If both the start date and the end date are imputed and if the imputed start date is after the imputed end date, use the imputed end date as the imputation for the start date.

##### Post therapies

###### Start date:

Imputed date = max (last date of study drug + 1, first day of the month), if day is missing;

Imputed date = max (last date of study drug + 1, 01JAN), if day and month are missing.

End date: No imputation.

#### 4.8.5 Incomplete assessment dates for tumor assessment

All investigation dates (e.g. X-ray, CT scan) must be completed with day, month and year.

If one or more investigation dates are incomplete but other investigation dates are available, the incomplete date(s) are not considered for calculation of the assessment date and assessment date is calculated as the latest of all investigation dates (e.g. X-ray, CT-scan) if the overall lesion response at that assessment is CR/PR/SD/UNK. Otherwise, if overall lesion response is PD, the assessment date is calculated as the earliest date of all investigation dates at that evaluation number. If all measurement dates have no day recorded, the 1st of the month is used.

If the month is not completed, for any of the investigations, the respective assessment will be considered to be at the date which is exactly between the previous and the following assessment. If both a previous and following assessments are not available, this assessment will not be used for any calculations.

In case of multiple imaging scans performed within an evaluation, if some imaging dates for tumor assessment under the same evaluation for a patient are before as well as after cut-off, the entire evaluation will not be included for analyses based on the pre-specified cut-off.

#### 4.8.6 Incomplete date for death

All dates must be completed with day, month and year.

If the day or month is missing, death date will be imputed to the maximum of the full (non-imputed) last contact date (excluding the date of death) and the following:

- Missing day: 1st day of the month and year of death
- Missing day and month: Jan 1st of the year of death

#### 4.8.7 Incomplete dates for last dose of study drug

##### Scenario 1

If the last date of study drug is after the cut-off date or is completely missing and there is no end of treatment eCRF page and no death date the patient should be considered to be on-going and use the cutoff date for the analysis as the last dosing date.

##### Scenario 2

If the last date of study drug is completely or partially missing and there is EITHER an end of treatment eCRF page OR a death date available then imputed last dose date:

= 31DECYYYY, if only Year is available and Year < Year of min (EOT visit date, death date)

= Last day of the month, if both Year and Month are available and EITHER

-- Year = Year of min (EOT visit date, death date) and Month < the month of min (EOT visit date, death date) OR,

-- Year < Year of min (EOT date, death date) irrespective of the month

= min (EOT visit date, death date), for all other cases.

The imputed date will be compared with start date of study drug.

If the imputed date < start date of study drug, then last date of study drug is set to start date of study drug;

Otherwise, use the imputed date.

#### 4.8.8 Incomplete dates for disease progression prior to start of study drug

If day of PD associated with prior antineoplastic medication is missing then imputed PD date:

= min (midpoint between the end date of the prior antineoplastic medication and the end of the month, start date of LDK, start date of prior medication from the next regimen), if end date of prior antineoplastic medication is in the same month as the PD date,

= min (15th of the month of the PD date, start date of LDK, start date of prior medication from the next regimen), if end date of prior antineoplastic medication is in a month prior to the PD date

= 15th of the month of the PD date, if end date of prior antineoplastic medication is in a month after the PD date.

[figure not shown]
If both day and month of PD associated with prior antineoplastic medication are missing then imputed PD date:

= min (midpoint between the end date of the prior antineoplastic medication and the end of the year, start date of LDK, start date of prior medication from the next regimen), if end date of prior antineoplastic medication is in the same year as the PD date

= min (July 1 of the year of the PD date, start date of LDK, start date of prior medication from the next regimen), if end date of prior antineoplastic medication is in a year prior to the PD date

= July 1 of the year of the PD date, if end date of prior antineoplastic medication is in a year after the PD date

Completely missing PD dates will not be imputed. The start date of medication from the next regimen is based on the earliest start date of any medication(s) from the next regimen. For the mid-point calculation, if odd days in between, (e.g. last dose of medication is 27 June 2012, and end of the month is 30 June 2012), then use the next day from the midpoint calculation (e.g. mid-point is 29 June 2013).

